#### 4.3 DISCONTINUATION FROM DOSING

Discontinuation from dosing means that the EOS visit is to be performed upon termination and indefinite monthly survival follow-up will be performed.

Subjects should be discontinued from dosing for the following reasons:

- Grade 3 toxicity considered by the Investigator to be at least "possibly" drugrelated that does not resolve to Grade ≤ 1 within 7 days following interruption of treatment.
- Need for > 1 dose reduction.
- Grade 4 toxicity considered by the Investigator to be at least "possibly" drug-related.
- Treatment interruption or delay for more than 14 days after the next scheduled dose due to an event unrelated to toxicity (e.g., intercurrent illness, scheduled surgery, etc.).
- Subject withdrawal of consent for trial participation at any time, for any reason, and without prejudice.
- Withdrawal of a subject by the Investigator, at his/her discretion, for any reason that the Investigator believes continuation of study drug therapy would not be in the subject's best interest. The reason for the subject's discontinuation must be recorded on the case report form (CRF).

- An intercurrent illness which, in the Investigator's opinion, would prevent completion of trial-related evaluations.
- Pregnancy.
- Subject noncompliance with trial or follow-up procedures.
- Termination of the trial by the Sponsor.

If a subject is withdrawn from treatment, the Investigator will make every effort to complete all final evaluations and laboratory tests required by the protocol. The reason(s) for discontinuation of dosing must be clearly documented on the CRF. Subjects who discontinue from dosing will be followed indefinitely for survival status.

#### 4.4 WITHDRAWAL FROM THE TRIAL

A subject will be considered to be withdrawn from the trial for the following reasons:

- Withdrawal of consent (in which every effort will be made to follow the subject for survival information);
- Termination of the trial by the Sponsor;
- Patient Death;
- Other.

#### 5. CLINICAL PROCEDURES AND ASSESSMENTS

The schedule of clinical procedures and assessments conducted during the study is presented in the following table. Further details are given in the protocol.

TABLE 1–1: SCHEDULE OF EVENTS FOR DOUBLE BLIND (DB) PERIOD

			Cycle 1	Subse Cy	quent cles	End of Study/ End of Dosing (EOS) 	Follow-Up
Trial Procedures	Pre-Study (-28 days)	Day 1 Baseline	Days 8 and 15 ± 2 days	Day 1 ± 2 days	Day 15 ± 2 days	Day 1 + 2 days	(28 ± 3 Days Post- EOS)
Medical history	X						
Physical examination	X a	$X^{a,c}$	$X^{b}$	$X^{b}$	$X^{b}$	$X^{b}$	$X^{a}$
Inclusion/exclusion criteria	X	X					
Informed consent	X						
Body weight	X	X c		X		X	X
Vital signs d	X	X	X	X	X	X	X
Clinical laboratory testing e	X	X c	X	X	X	X	X
T3. T4, TSH	X	X		X		X	X
ECG f	X	X	X	X	X	X	X
Pregnancy test (serum) g	X	X c		X		X	X
ECOG PS g	X	X c		X		X	
α-fetoprotein (AFP)		X		X		X	X
WBC A3AR sample		X		$X^h$			
PK samples		$X^k$	$X^k$	$X^k$			
Hepatitis B/C virus serology	X						
Hepatitis B/C viral load (if		X		X i		X i	
seropositive)		Λ		Λ		Λ	
Tumor imaging for RECIST	$X^{j}$			$X^{j}$		X	
Concomitant medications	X	X	X	X	X	X	X
Adverse events		X	X	X	X	X	X
Dispense study drug supplies		X		X			
Review treatment compliance		X	X	X	X	X	

Symptom-directed examination.

c If Pre-Study assessment was performed \le 3 days prior to the Baseline Visit, assessments do not need to be repeated prior to

d Temperature, pulse, respiration, blood pressure at: Pre-Study; pre-dose at all visits; at 1, 2, 3, 4h (± 5 min), 6 and 8h (± 10 min) post-dose on Cycle 1 Day 1; and at Follow-up.

e See list of parameters in Appendix C.

FECG at Pre-Study; pre-dose at all visits; and at 2, 4, and 8h (± 10 min) post-dose on Cycle 1 Day 1; and at Follow-up.

Performed at Pre-Study, prior to the first dose, at the end of each cycle, and at Follow-up.

Day 1 of odd-numbered cycles, unless waived by the Sponsor (selected sites only).

For subjects with measurable viral load at the Baseline Visit; on Day 1 of odd-numbered cycles only and at EOS.

To subjects with heasthable vital load at the Baseline Visit, on Day 1 of odd-humbered cycles only and at EOS.

CT scan or MRI at Pre-Study, the end of Cycle 2, and at the end of subsequent even-numbered cycles. For trial eligibility purposes, a scan performed ≤ 21 days prior to the Pre- Study Visit may be used (allowed time window is of -7/+1 day with respect to day 28 of each even numbered cycles; if performed at +1 day after day 28, CT/MRI scan must be performed before administration of the morning dose of that day)

k Sparse sampling on Day 1 of Cycles 1 and 2 only. Pre-dose trough samples on Cycle 1 Days 8 and 15 only. See Table 10-1 of

the protocol for PK sampling time points.

End of Study visit timeframe is of 2 days since the last administered dose of IMP/matching Placebo.

<sup>a Complete PE performed at the Pre-Study (and/or the Baseline Visit if performed > 3 days prior to first dose) and End of Study/End of Dosing (EOS) visits.

TABLE 1–2: SCHEDULE OF EVENTS FOR OPEN LABEL (OL) PERIOD

	OL	Cycle 1	Subsequen	t OL Cycle	OL End of Study/End of Dosing (EOS) j	OL Follow- up (28 ± 3
Trial Procedures	Day 1 Baseline	Days 8 and 15 ± 2 Days	Day 1 ± 2 Days	Day 15 ± 2 Days	Day 1 ± 2 Days	Days Post EOS)
Physical examination	$X^{b}$	X b	$X^{b}$	$X^b$	$X^{a}$	$X^b$
Eligibility criteria for OL	X					
Informed consent for OL	X					
Body weight	X		X		X	X
Vital signs c	X	X	X	X	X	X
Clinical laboratory testing d	X	X	X	X	X	X
T3, T4, TSH	X		X		X	X
ECG e	X	X	X	X	X	X
Pregnancy test (serum) f	X		X		X	X
ECOG PS f	X		X		X	
α-fetoprotein (AFP)	X		X		X	X
WBC A 3 AR sample	X		$X^g$			
Hepatitis B/C viral load (if seropositive)	X		$X^h$		$X^h$	
Tumor imaging for RECIST			$X^{i}$		X	
Concomitant medications	X	X	X	X	X	X
Adverse events	X	X	X	X	X	X
Dispense study drug supplies	X		X			
Review treatment compliance	X	X	X	X	X	

a. Complete PE performed at Open Label (OL) End of Study/OL End of Dosing (EOS) visits.

- b. Symptom-directed physical examination.
- c. Temperature, pulse, respiration, blood pressure performed at the following times: pre-dose at all visits; at 1, 2, 3, 4h ( $\pm$  5 min), 6h and 8h ( $\pm$  10 min) post-dose on OL Cycle 1 Day 1 and at OL Follow-up.
- d. See list of parameters in Appendix C.
- e. ECG at pre-dose at all visits; and at 2, 4, and 6h (± 10 min) post-dose on OL Cycle 1 Days 1 and 8; and at OL Follow-up.
- f. Performed pre-dose on Day 1 of each OL cycle, and at OL Follow-up.
- g. Day 1 of odd-numbered cycles, unless waived by the Sponsor (selected sites only).
- h. For subjects with measurable viral load at the Baseline Visit; on Day 1 of OL odd-numbered cycles only and at OL EOS.
- i. CT scan or MRI at the end of OL even-numbered cycles. If performed at +1 day after day 28, CT/MRI scan must be performed before administration of the morning dose of that day).
- j. End of Study OL visit timeframe is of 2 days since the last administered dose of IMP.

#### 6. STUDY ENDPOINTS

Baseline typically refers to Day 1 of Cycle 1 and Screening refers to the Pre-Study Visit. For some variables, Baseline is Cycle 1 Day 1 unless the assessment was performed at Screening which was  $\leq 3$  days prior to Cycle 1 Day 1, in which case the assessment was not to be repeated (footnotes 'a' and 'c' of Table 1-1). In the protocol and footnotes above, some assessments are given as performed at Day 28 or 29 of a cycle; consistent with the table above and the CRFs, these assessments are described below as being performed at Day 1 of the following cycle.

Tumor assessments performed at the End of Study/ End of Dosing (EOS) Visit, the Follow-up Visit, and Unscheduled Visits will be assigned to the next cycle for calculation of summary statistics.

The subjects who are still on blinded treatment when Amendment 5 is approved will be switched to open-label treatment at their next scheduled visit. The first day of open-label study drug dosing will be considered Day 1 (OL) of the trial. During this visit, the OL Cycle 1 Day 1 for OL procedures will be performed ( $\underline{\text{Table 1-2}}$ ). During the OL period, clinic visits will take place within  $\pm$  2 working days of the scheduled day; during these visits, assessments will be performed prior to administration of the study drug dose for that day.

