9.3.5 Subsequent Cycles Day 15 Visit (± 2 days)

The following assessments will be performed prior to the daily dose of study drug:

- Physical examination (symptom-directed)
- Vital signs (Section 9.2.6)
- Laboratory assessments (Section 9.2.8)
- ECG pre-dose (Section 9.2.10)
- Concomitant medications
- Adverse events
- Review treatment compliance

9.3.6 End of Study/End of Dosing (EOS) Visit (within 2 days of last dose)

- Physical examination (complete examination)
- Vital signs (Section 9.2.6)
- Laboratory assessments including thyroid functions (Section 9.2.8)
- Serum β -hCG pregnancy test (Section 9.2.8) if indicated
- ECG (Section 9.2.10)
- ECOG PS (Section 9.2.5)
- AFP
- Hepatitis B and/or C viral load (for subjects with measurable viral load at the Baseline Visit)
- Tumor imaging for RECIST (Appendix A)
- Concomitant medications

- Adverse events
- Review treatment compliance and collect all used study drug supplies

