4.4.3. Best overall response: all time points

The best overall response is determined once all the data for the patient is known.

Best response determination in trials where confirmation of complete or partial response IS NOT required: Best response in these trials is defined as the best response across all time points (for example, a patient who has SD at first assessment, PR at second assessment, and PD on last assessment has a best overall response of PR). When SD is believed to be best response, it must also meet the protocol specified minimum time from baseline. If the minimum time is not met when SD is otherwise the best time point response, the patient’s best response depends on the subsequent assessments. For example, a patient who has SD at first assessment, PD at second and does not meet minimum duration for SD, will have a best response of PD. The same patient lost to follow-up after the first SD assessment would be considered inevaluable.

Table 1 – Time point response: patients with target (+/– non-target) disease.

Target lesions	Non-target lesions	New lesions	Overall response
CR	CR	No	CR
CR	Non-CR/non-PD	No	PR
CR	Not evaluated	No	PR
PR	Non-PD or not all evaluated	No	PR
SD	Non-PD or not all evaluated	No	SD
Not all evaluated	Non-PD	No	NE
PD	Any	Yes or No	PD
Any	PD	Yes or No	PD
Any	Any	Yes	PD

CR = complete response, PR = partial response, SD = stable disease, PD = progressive disease, and NE = inevaluable.

Table 2 – Time point response: patients with non-target disease only.

Non-target lesions	New lesions	Overall response
CR	No	CR
Non-CR/non-PD	No	Non-CR/non-PD ^a
Not all evaluated	No	NE
Unequivocal PD	Yes or No	PD
Any	Yes	PD

CR = complete response, PD = progressive disease, and NE = inevaluable.
^a 'Non-CR/non-PD' is preferred over 'stable disease' for non-target disease since SD is increasingly used as endpoint for assessment of efficacy in some trials so to assign this category when no lesions can be measured is not advised.

Best response determination in trials where confirmation of complete or partial response IS required: Complete or partial responses may be claimed only if the criteria for each are met

at a subsequent time point as specified in the protocol (generally 4 weeks later). In this circumstance, the best overall response can be interpreted as in Table 3.

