4.6. Confirmatory measurement/duration of response

4.6.1. Confirmation

In non-randomised trials where response is the primary endpoint, confirmation of PR and CR is required to ensure responses identified are not the result of measurement error. This will also permit appropriate interpretation of results in the context of historical data where response has traditionally required confirmation in such trials (see the paper by Bogaerts et al. in this Special Issue¹⁰). However, in all other circum-

stances, i.e. in randomised trials (phase II or III) or studies where stable disease or progression are the primary endpoints, confirmation of response is not required since it will not add value to the interpretation of trial results. However, elimination of the requirement for response confirmation may increase the importance of central review to protect against bias, in particular in studies which are not blinded.

In the case of SD, measurements must have met the SD criteria at least once after study entry at a minimum interval (in general not less than 6–8 weeks) that is defined in the study protocol.

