#### **6.1.2** TUMOR RESPONSE

The secondary endpoints which are based directly on tumor response are:

- ORR (OR Rate): proportion of subjects who have CR or PR,
- DCR (DC Rate): proportion of subjects who have CR, PR, or SD, and
- Best Overall Response during the duration of the study.
   (The best overall response for each subject is the best response recorded from the start of the study treatment until the end of study, in the order of CR, PR, SD, or PD from best to worst.)

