#### 7.2 GENERAL ANALYSIS

The following standards will be applied for analyses unless otherwise specified. Simple descriptive statistics for continuous data are: n (number of non-missing observations), mean, standard deviation, maximum, median, and minimum. Categorical data will be summarized by the number and percentage of subjects in each category. Summaries of efficacy variables will be presented by visit through end of Cycle 11. Best Overall Response will be summarized once for the entire study. All data will be listed for the Safety Population, sorted by investigator number, subject number and, where appropriate, by visit, including data from visits after Cycle 11. The choice of Cycle 11 as the final time for tabulation will be finalized prior to unblinding. Tumor assessments performed at the EOS Visit, the Follow-up Visit, and Unscheduled Visits will be assigned to the next cycle and will be analyzed with that cycle. Tumor responses recorded on the CRF will be listed. Other data from Unscheduled Visits will not be summarized, except for AEs.

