#### 7.6.4 TUMOR RESPONSE

The Objective Response Rate (ORR) is the percentage of subjects who achieved either CR or PR. ORR will be summarized using counts and percentages for the ITT Population by treatment and cycle. The between-treatment comparison will be performed using the normal approximation to the binomial distribution (NAB) with unequal variances, as follows.

For each cycle, let  $p_{CF}$  and  $p_0$  denote the proportions of subjects who experienced CR or PR based on  $n_{CF}$  and  $n_0$  subjects for CF102 and Placebo, respectively, and let

 $Z=(p_{CF}-p_0)/(p_{CF}(1-p_{CF})/n_{CF}+p_0(1-p_0)/n_0)^{1/2}$ .

Then the corresponding p-value is p=2\*(1-PROBNORM(ABS(Z))).

The Disease Control Rate (DCR) is the percentage of subjects who achieved either CR, PR, or SD. DCR will be summarized using counts and percentages for the ITT Population by treatment and cycle. The between-treatment comparison will be performed using the (NAB), similar to that for ORR.

For each subject, the Best Overall Response during the duration of the study will be determined and will be summarized using counts and percentages for the ITT Population by treatment. The between-treatment comparison will be performed using the NAB, for both the percentage of subjects who achieved either CR or PR (similar to ORR) and the percentage of subjects who achieved either CR, PR, or SD (similar to DCR).

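### Stable disease counts toward Best Overall Response and its disease control rate with no minimum time from baseline, so a subject who stops in the first weeks without progression is scored as disease control

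*SAP*

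**What the plan says.** **Response rules in the SAP.** Section 6.1.2 defines Best Overall Response: "The best overall response for each subject is the best response recorded from the start of the study treatment until the end of study", ranked "in the order of CR, PR, SD, or PD from best to worst". Section 7.6.4 states: "The Disease Control Rate (DCR) is the percentage of subjects who achieved either CR, PR, or SD". It then applies the same between-arm test to DCR by cycle and to the CR, PR or SD percentage based on Best Overall Response. Appendix B repeats the DCR definition. None of these carries a time condition.

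**When scans happen.** The first scheduled on-treatment scan is at the end of Cycle 2, with a window of 7 days before to 1 day after (Protocol Table 1-1, footnote j). Protocol 9.3.6 also lists "Tumor imaging for RECIST" among the End of Study (EOS) procedures, within 2 days of the last dose, with no exemption for an early stop.

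**Which cycle a scan belongs to.** SAP Section 6 says that EOS, Follow-up and Unscheduled tumour assessments "will be assigned to the next cycle for calculation of summary statistics". Section 7.2 says that they "will be assigned to the next cycle and will be analyzed with that cycle".

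**The adopted criteria.** SAP Section 6.1 and Appendix B apply RECIST 1.1 as reproduced in Protocol Appendix A. Section 4.4.3 of that paper says: "When SD is believed to be best response, it must also meet the protocol specified minimum time from baseline". It treats a subject lost after one SD scan that falls short of the minimum as inevaluable. Section 4.6.1 requires SD to have been met at least once "at a minimum interval (in general not less than 6–8 weeks) that is defined in the study protocol". The protocol body (9.2.12) only refers back to the appendix for SD duration.

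**The concern.** RECIST hands the number to the protocol, and the visible protocol and SAP text never supply it. Best Overall Response then takes SD at face value from a scan of any date. SAP Section 9 does not list this as a departure.

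DCR is a named secondary objective with a between-arm p-value. In the earlier CF102 trial the best response was SD, in 5 of 17 subjects (Protocol 4.2.2), so DCR here is likely to be mainly an SD rate. The protocol also expects median survival of about 2 months or less after sorafenib failure (4.5.2), so early exits are plausible. If early SD counts, DCR depends partly on when subjects stop and whether they are scanned at that point. Balanced early stopping inflates both arms. Unbalanced early stopping distorts the comparison in either direction.

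**Working it through.** **The plan's own figure.** The documents give no design figure for DCR. The only one is 75 deaths for HR 0.5, 80% power, two-sided 0.05 and 2:1 allocation. Schoenfeld: (1.960 + 0.842)² / [(2/9)(ln 0.5)²] = 73.5, so 74 deaths; 75 give power 0.808. It reproduces, and this point does not touch it.

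**The scan window, in days after Cycle 1 Day 1.**
- Nominal: day 28 of Cycle 2 is study day 56. Less 7 is study day 49, which is 48 days after Cycle 1 Day 1.
- If Cycle 2 Day 1 is 2 days early (study day 27), day 28 of Cycle 2 is study day 54. The window then opens on study day 47, 46 days after.
- A scan 14 to 21 days after Cycle 1 Day 1 is 27 to 34 days before the nominal window opens, and 21 to 28 days short of 6 weeks.

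**One subject traced through the rules.** The subject has measurable disease, takes a last dose in week 3, and has an EOS scan with no PD and no response.
- Best Overall Response: SD is the best response recorded, so the subject is a DCR success. The next-cycle rule plays no part.
- Under Appendix A with a 6-week minimum: one early SD and no later scan is inevaluable.
- By-cycle DCR: the cycle after Cycle 1 is literally Cycle 2, which has no scheduled scan, and the shell for Table 14.2.2.1.1 starts at Cycle 3 Day 1. The SD appears there only if the rule means the next imaging cycle. The meaning matters only for Cycle 1 stops; a stop in Cycle 2 goes to Cycle 3 either way.

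**Effect per subject.** 78 subjects at 2:1 are 52 and 26. The percentage denominator is the ITT Population in each arm (Table 14.2.2.2.1 footnote). 1/52 = 1.9 points; 1/26 = 3.8 points.

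**Upper bound on early stops.** Assume exponential time on drug with median m months (30.44 days per month). The documents give no such median. P(stop before day d) = 1 − 0.5^(d / (30.44 m)).

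| d | m = 2 | m = 3 | m = 4 | m = 6 |
|---|---|---|---|---|
| 21 | 21% | 15% | 11% | 8% |
| 42 | 38% | 27% | 21% | 15% |
| 49 | 43% | 31% | 24% | 17% |

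These are all stops, including subjects who die, progress or have no scan.

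**Illustration of the comparison.** Assume disease control meeting the minimum in 15/52 and 7/26, add early SDs, and apply the unequal-variance Z of SAP 7.6.4 with ITT denominators.

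| Early SD (CF102, placebo) | DCR CF102 | DCR placebo | Z | p |
|---|---|---|---|---|
| 0, 0 | 28.8% | 26.9% | 0.18 | 0.858 |
| 8, 0 | 44.2% | 26.9% | 1.56 | 0.119 |
| 8, 4 | 44.2% | 42.3% | 0.16 | 0.871 |
| 2, 4 | 32.7% | 42.3% | −0.82 | 0.410 |

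The counts are invented to show the mechanism.

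**The case against.** **The next-cycle rule.** A reader might infer that this rule produces the effect and inflates every DCR table. The documents do not support that. Best Overall Response does not use the rule, and on a literal reading a Cycle 1 stop goes to a cycle that the table does not show. What stands is that the meaning needs stating.

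**Text that could not be read.** The rest of the target-lesion response table in SAP Appendix B, after the PR row, and the Tumor Response listing shells (16.2.6.3.1 and 16.2.6.3.2) were not in the text available. An SD minimum might appear there. The point is therefore limited to the visible text. The SD definition in RECIST 4.3.1, as reproduced in the protocol, has no time element.

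**RECIST already covers it.** The SAP cites the appendix, the appendix says 6–8 weeks in general, and Appendix B offers a not-evaluable (NE) category. But the appendix leaves the value to the protocol, and no visible rule sends an early SD to NE. A programmer following 6.1.2 would score SD.

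**Stakes and timing.** DCR is a secondary endpoint outside the power calculation, and the same rule applies to both blinded arms. This SAP version already contains decisions made after unblinding, so redefining DCR now is a post-unblinding change. Both points are fair. They call for disclosure and for results under both rules, not for leaving the conflict in place.

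**Conclusion.** The point holds for Best Overall Response and its DCR. The visible rule scores an early non-progressing EOS scan as disease control, and the adopted criteria would not once a minimum is set. For a stop in Cycle 1, by-cycle DCR is affected only if the next cycle means the next imaging cycle.

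The documents do not give the size. The 17–43% stopping before day 49 is an upper bound under assumed exponential medians of 6 to 2 months. A reader might take it as the share misclassified, but it includes deaths, progressions and subjects never scanned. Non-target-only disease also falls outside, because Appendix B rates it Non-CR/non-PD, which DCR does not count. What is firm is the per-subject effect: about 1.9 points on CF102 and 3.8 on placebo.

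A reader might also infer a bias toward CF102. The documents do not support one, since the direction depends on which arm has more early stops with a scan. OS is unaffected, and TTP and PFS run on actual dates.

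**What to change.** In SAP 6.1.2, 7.6.4 and Appendix B:

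- Count SD toward DCR and Best Overall Response only if the scan is at least 6 weeks (42 days) after Cycle 1 Day 1. This admits every in-window first scheduled scan (48 days after Day 1 nominally, 46 with an early Cycle 2 visit). A cut-off of 49 days after Day 1 would reject permitted scans.
- Class an earlier scan showing neither PD nor response, with no later scan, as NE. Keep the subject in the ITT denominator as a non-responder, and add an NE row to the response table shells.

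In SAP 6 and 7.2, assign EOS, Follow-up and Unscheduled scans to an imaging cycle by actual scan date.

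Record the change in SAP Section 9 as made after unblinding, and report DCR under the current rule beside it.

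The cost is a small date derivation from assessment dates already listed (Listing 16.2.6.1.1), an extra set of DCR results, and a slightly lower DCR.
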